Impact of Plant Sterol Supplement on LDL-C Lowering in Low-to-Moderate Risk South Asian Patients Participating in a Cardiovascular Disease Prevention Program

Study Protocol and Statistical Analysis Plan

NCT04030247

June 25, 2020

Title: Impact of Plant Sterol Supplement on LDL-C Lowering in Low-to-Moderate Risk South Asian Patients Participating in a Cardiovascular Disease Prevention Program

PI: [name] PhD
Asst Prof, Stanford University Medical Center
Medical & Scientific Director, SSATHI Clinic
Medical Director, CardioClick Telemedicine Clinic

Sites (2): - Stanford SSATHI Clinic, [name]
- Main Cardiology Clinic, [name]

Purpose:

The purpose of this study is to measure the effectiveness of a twice daily plant sterol supplement, which is in a gummy format and packaged with health insights, in a population of South Asian patients who have low to moderate cardiovascular disease (CVD) risk by traditional risk scoring. Defined as a 10-year cardiovascular risk score (ASCVD Score) of < 7.5%, and a LDL-C level of 120-189mg/dl, these individuals do not meet guideline-based criteria (2018 ACC/AHA Lipid Guidelines) for medical lowering of their LDL-C with an HMG CoA reductase inhibitor (statin) drug, and they are recommended to improve their lipid-risk profile through diet and exercise primarily. Additional lipid lowering is routinely desired yet often never achieved solely through a lifestyle approach. In addition, patients who may qualify for statin therapy, those with ASCVD score > 7.5% or LDL > 189 mg/dl, but are deemed to be intolerant of statins or who refused lipid lowering medication may also qualify. While the safety and benefits of plant sterol supplements have been established and are incorporated into many lipid lowering guidelines, their effects have not been measured in the highest CVD risk population in the world, namely South Asians. In this study, we aim to measure the LDL-C reducing impact of regular plant sterol supplementation for these low-to-moderate risk South Asians.

The Clinic

Founded in 2014, the Stanford South Asian Translational Heart Initiative (SSATHI) is the only preventive cardiology clinic in the U.S. dedicated to exclusively treating South Asian patients for both traditional and non-traditional cardiovascular risk factors. The clinic includes an intensive program combining physician visits and serial laboratory testing. The patients also benefit from frequent dietitian/health coach visits during the program, all of which are conducted virtually through SSATHI's telehealth arm, CardioClick. Typically, lipid lowering effects from lifestyle changes are manifest within 3 months. In this proposal, the study length will be 3 months for each enrolled subject.

Study Design

This single arm study will include one in-person or video baseline visit, with a virtual follow up visit with the treating physician.

At the baseline visit, subjects will complete informed consent, a medical history, and clinic visit procedures, inclusion/exclusion criteria, medication review, measurement of morphometrics (body weight, height, BMI, hip and waist circumference, blood pressure, heart rate). A fasting blood draw for baseline labs will be performed within 8 weeks of start date. Women under 60 years will receive a urine pregnancy test. We are washing out any lipid lowering non prescription medications.

There will also be focused patient engagement questionnaires administered at the end of the study.

Intervention

Enrolled subjects, upon completion of the baseline clinical and laboratory assessment, will be given a 90 day supply of gummy plant sterol supplements in daily packets, totaling 1400 mg of daily plant sterol to be ingested in two daily doses. During the 90 day treatment, subjects will be contacted weekly through Twilio or SMS messaging by the research team to assess compliance which requires a single digit response from each subject to report compliance with the gummy sterol treatment. At the end of the study, a virtual clinical visit and laboratory test, along with post-study surveys, will be administered.

Baseline visit

- Informed consent/HIPAA
- Medical history
- Clinic visit
 - Baseline measurements, lab testing
 - Assess prior and current medication/supplement use
 - Review inclusion/exclusion criteria
- Diet assessment
- Fasting Lipid profile
- In-clinic urine pregnancy test for female subjects, if applicable
- Dispense study product
- Provide study instructions

Regular product compliance assessment

- Weekly Twilio or SMS text messaging question with a numeric response to assess product compliance

End of Study Visit

- Assess prior and current medication/supplement use
- Fasting Lipid profile
- Questionnaire
 - SSATHI questionnaire
 - Sponsor questionnaire
- Assess product compliance
- Assess adverse events

Inclusion Criteria

1. Subject is a South Asian male or female, ≥ 18 years of age
2. Subject has LDL-C ≥ 120 and < 190 mg/dL measured in the past 3 months (or measured at the baseline visit), while not taking cholesterol-lowering medication or cholesterol-lowering supplement for at least 1 month prior, and having a ASCVD Risk score $< 7.5\%$.
3. Subjects with LDL-C ≥ 120 and < 190 mg/dL with ASCVD risk scores $> 7.5\%$ who are known to be intolerant of statin therapy drugs.
4. Subjects with LDL-C > 189 mg/dL or ASCVD $> 7.5\%$ who have declined prescription medical therapy.
5. If current smoker, subject does not have any plans to change current smoking status or frequency.
6. Subject is willing to fast (10-14 h, target 12 h, water only) prior to each clinic visit.
7. Subject understands the study procedures and signs forms documenting informed consent to participate in the study and authorization for release of relevant protected health information to the study Investigator and is willing to complete study procedures.
8. Subject is agreeable to receiving clinical care virtually.

Exclusion Criteria

1. Subject has taken a prescription cholesterol-lowering medication in the past 1 month.
2. Subject has a known allergy or sensitivity to soy, corn, or other ingredients in the study product.
3. Subject is taking dietary supplements for cholesterol-lowering such as red yeast rice, niacin > 100 mg/d or omega-3 fatty acid supplements providing ≥ 1000 mg/d eicosapentaenoic acid and/or docosahexaenoic acid. (Stable use of viscous fiber laxative ≤ 2 teaspoons/d is allowed.)
4. Subject is a female, who is pregnant, planning to be pregnant during the study period, or lactating. Subjects should agree to use contraception during study period to avoid pregnancy.

5. Individual has active angina, stable or unstable, requiring urgent cardiovascular functional risk stratification (stress testing or catheterization) or intervention. Or has congestive heart failure that is not compensated or in which the subject is not euvolemic, as determined by the treating MD.
6. Individual has a condition the Investigator believes would interfere with his or her ability to provide informed consent, comply with the study protocol, which might confound the interpretation of the study results or put the person at undue risk.

Primary Outcome

% change in LDL Direct, or LDL-C if LDL Direct is not available, from baseline at 3 months

Exploratory Outcomes

% changes from baseline to 3 months in following:

- Total cholesterol
- Calculated LDL-C or LDL Direct
- HDL-C
- Non-HDL-C
- Triglycerides
- Fasting Glucose
- Fasting Insulin
- Hba1c
- Lp(a)
- Apoprotein B-100
- Apoprotein A1
- Ratio, ApoB-100/Apo A1
- C-reactive protein

Changes from baseline to 3 months in questionnaire metrics of patient engagement, satisfaction, and outlook on health

Product compliance

Subjects' interest in continuing to use product

Statistical Analysis

Because of the pre-post nature of this single group study, either a paired t-test or a non-parametric paired test will be employed to analyze the statistical significance of any differences at the end of the study. This decision will depend upon the normality of the data set.

Sample Size

A sample size of 50 will be enrolled. Our population exhibits a standard deviation of 25mg/dl in baseline LDL-C, the primary outcome variable. As a result, an evaluable sample of 40 subjects will provide 80% power to detect a difference of 10% based on a paired t-test and a two-sided alpha of 0.05. A larger enrolled sample will allow for subject attrition of up to 20%.

Statistical Analysis

Baseline characteristics will be described using means and standard deviations or medians and interquartile range limits as appropriate based on the distribution for continuous variables. Numbers of subjects and percentages will be used to describe categorical variables. Responses to the intervention will be assessed using paired t-tests for continuous variables. For categorical variables, McNemar's test will be employed to assess differences in frequencies between baseline and end-of-study. All tests of statistical significance will be completed using alpha = 0.05, two-sided.

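### The title and aim name low-to-moderate risk subjects, but the only planned analysis pools them with an uncapped number of higher-risk entrants, so its result describes everyone enrolled

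*Combined protocol and SAP*

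**What the plan says.** All references are to the combined protocol and SAP.

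- **Title:** "Impact of Plant Sterol Supplement on LDL-C Lowering in Low-to-Moderate Risk South Asian Patients".
- **Purpose, definition:** "Defined as a 10-year cardiovascular risk score (ASCVD Score) of < 7.5%, and a LDL-C level of 120-189mg/dl".
- **Purpose, wider entry:** the same paragraph then adds patients who may qualify for a statin, "those with ASCVD score > 7.5% or LDL > 189 mg/dl, but are deemed to be intolerant of statins or who refused lipid lowering medication".
- **Purpose, aim:** the paragraph closes with "we aim to measure the LDL-C reducing impact of regular plant sterol supplementation for these low-to-moderate risk South Asians".
- **Inclusion Criteria:** item 2 matches the definition. Item 3 takes LDL-C from 120 to below 190 mg/dL with ASCVD above 7.5% in subjects "who are known to be intolerant of statin therapy drugs". Item 4 begins "Subjects with LDL-C > 189 mg/dL or ASCVD", continues with a score above 7.5%, and applies to those who declined prescription therapy. No section limits the number entering by item 3 or 4. Read literally, item 4 sets no upper LDL-C limit, and no lower one for a subject who enters on the ASCVD score.
- **Primary Outcome:** percent "change in LDL Direct, or LDL-C if LDL Direct is not available, from baseline at 3 months", without restriction to a risk group.
- **Statistical Analysis and Sample Size:** one single-group paired comparison, with one sample size of 40 evaluable out of 50 enrolled. No stratified, subgroup or sensitivity analysis by risk group is planned.

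**The concern.** Entry was widened but the claim was not. Followed as written, the plan would attach a conclusion about low-to-moderate risk South Asians to an average over a mixed group whose composition depends on who happens to enrol. Subjects with a statin indication who cannot or will not take one might differ from the defined group in baseline LDL-C, motivation, adherence, or the chance of starting another drug. The documents do not say whether they do. If percent response differed, a single pooled mean could not show it, and a reader would have no planned result for the population in the title.

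**Working it through.** **1. The plan's own figure.** Enrolment follows from the attrition allowance: 40/(1 − 0.20) = 50. The 40 itself cannot be settled, because the mean baseline LDL-C and the SD of the paired change are not given (25 mg/dL is the SD of baseline values). If the paired change had an SD of 25 mg/dL, 40 subjects at 80% power would detect 11.4 mg/dL, which is 10% of 114 mg/dL. With uncorrelated measurements (SD 25 × √2 = 35.4) and a mean of 160 mg/dL, a 10% fall gives 79.7% power. The 40 is thus attainable under some unstated assumptions. This point does not need it to be wrong.

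**2. What the pooled mean estimates.** Let *f* be the share entering by criteria 3-4, *T* the mean percent fall in criterion-2 subjects and *O* the mean percent fall in the others:

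pooled = (1 − f)·T + f·O, so pooled − T = f·(O − T).

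The departure is zero if O = T. Neither *f* nor O − T is in the documents. With assumed values f = 0.25 to 0.50 and O − T = 5 points, it is 0.25 × 5 = 1.25 to 0.50 × 5 = 2.5 points. At f = 0.50, three different situations give the same pooled 10% fall:

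| T | O | 0.5·T + 0.5·O |
|---|---|---|
| 10 | 10 | 10 |
| 5 | 15 | 10 |
| 0 | 20 | 10 |

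The planned analysis cannot tell these apart.

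**3. Precision of a criterion-2 estimate.** Assume 20-30 of 40 evaluable subjects meet criterion 2, with the same SD. The CI width ratio is (t₀.₉₇₅,ₙ₋₁/√n) / (t₀.₉₇₅,₃₉/√40), with t₃₉ = 2.023:

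- n = 30: (2.045/2.023) × √(40/30) = 1.011 × 1.155 = 1.17.
- n = 20: (2.093/2.023) × √(40/20) = 1.035 × 1.414 = 1.46.

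**4. Power in that subset.** Fix the effect so that 40 subjects give exactly 80% power (two-sided 0.05, noncentral t). Power is then 70% with 32 subjects (f = 20%), 57% with 24 (f = 40%) and 49% with 20 (f = 50%).

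**5. Would the subset estimate be more accurate?** Read the planned difference as 10 percentage points. Power of 80% with 40 subjects then implies a standardised effect of 0.454 and an SD of percent change of 10/0.454 ≈ 22 points. The root mean squared error for *T*, under the assumed 5-point difference, is:

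| f | pooled, n = 40 | criterion 2 only |
|---|---|---|
| 25% | √(22²/40 + 1.25²) = 3.7 | √(22²/30) = 4.0 |
| 50% | √(22²/40 + 2.5²) = 4.3 | √(22²/20) = 4.9 |

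The order reverses when SD² × (1/30 − 1/40) < 1.25², that is SD below 13.7, or when SD² × (1/20 − 1/40) < 2.5², that is SD below 15.8.

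**The case against.** The strongest reply is that this is a matter of labelling. The Purpose announces the wider entry before it states the aim, and criteria 3-4 carry it out, so eligibility and analysis agree with each other. A reader might infer a concealed change of population. The documents do not support that: what lags is the title and one sentence.

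Second, nothing in the documents says that percent LDL-C response varies with ASCVD score or with refusal of a statin, and a percent-change outcome already scales for baseline level. The first part stands. The second stands only in part, because scaling does not remove regression to the mean in a single-arm study that selects on LDL-C. Take an assumed population mean of 130 mg/dL and a test-retest correlation of 0.7-0.9. The apparent fall with no treatment effect is then (1 − correlation) × (entry − 130)/entry, which is 1.3-4.0% at an entry value of 150 and 3.5-10.5% at 200. This operates where the qualifying value also serves as baseline, and it concerns the high LDL-C entrants, not those who enter on ASCVD score alone. It shows that equal response cannot be taken for granted, not that response differs.

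Third, the illustrated shift of 1.25-2.5 points is small beside the pooled 95% CI half-width at the implied SD, 2.023 × 22/√40 = 7.0 points, and the subset estimate then has the larger root mean squared error. This stands. It rules out the tempting step of replacing the primary analysis with the criterion-2 analysis.

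Fourth, the baseline visit already reviews eligibility, so entry status should be recoverable. That is so, but a subset chosen for analysis after results are known carries less weight than one fixed in advance.

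**Conclusion.** The mismatch is plain on the text: the title and aim name a defined group, entry goes beyond that group without a cap, and one pooled test is all that is planned. The pooled result is a valid before-after summary for all enrolled South Asian subjects. It answers for low-to-moderate risk subjects only on the untested assumption of similar percent response across entry groups.

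A reader might go further and infer that the primary estimate is biased by some stated amount. The documents do not support that, since they give neither the mix nor the responses by group; the 1.25-2.5 points are illustration only. Nor does the point show that the sample size is wrong. This is a modest, cheaply corrected weakness in what the trial can conclude.

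**What to change.** 1. Keep the all-subjects paired analysis as the single primary test at alpha 0.05; it governs the conclusion.
2. Reword the title, aim and primary conclusion to the population actually enrolled.
3. Report the number of subjects entering by each of criteria 2, 3 and 4.
4. Pre-specify one supportive estimate, the mean percent change with 95% CI in criterion-2 subjects, with no separate significance claim. Use the low-to-moderate risk label only for that estimate.

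The cost is a narrower headline claim, some wording in the protocol and SAP, and one extra estimate from data already collected. Eligibility, treatment and sample size are unchanged. The supportive estimate is less precise and is not covered by the stated power. Restoring 40 evaluable criterion-2 subjects would take 50/(1 − f) enrolled, for example 50/0.5 = 100 at f = 50%, and this is not asked for.

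### Cheap improvement: adverse events are solicited only at the End of Study Visit, so a subject who leaves before it is not asked about events or the reason for stopping

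*Combined protocol and SAP*

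**What the plan says.** Study Design sets out one baseline visit and one virtual follow-up visit. Intervention supplies 90 days of product and describes the close of the study: "At the end of the study, a virtual clinical visit and laboratory test, along with post-study surveys, will be administered". The End of Study Visit list ends with "Assess adverse events". No other visit list, and no other section, contains an adverse event step.

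Between the two visits the schedule has one kind of contact, listed under Regular product compliance assessment: "Weekly Twilio or SMS text messaging question with a numeric response to assess product compliance". Intervention says that this text "requires a single digit response from each subject to report compliance with the gummy sterol treatment". It is not described as asking about symptoms.

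The document describes no early-termination visit, no contact at discontinuation and no recording of the reason for stopping. Sample Size allows for the loss of up to 20% of enrolled subjects. Adverse events are not among the primary or exploratory outcomes, and neither Statistical Analysis section mentions them.

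**The concern.** The subjects most likely to have stopped because of an adverse event are those who leave early, and the schedule has no step that asks them. Adverse events would then be solicited only from those who reach the last visit. A summary of the responses would describe the subjects who stayed, and a reader could take it to describe everyone who was dosed.

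The reason for stopping is lost in the same way. It would help in interpreting two listed exploratory outcomes: product compliance and interest in continuing the product. At stake are the completeness of adverse event capture and the interpretation of early stopping. No planned efficacy conclusion is at stake.

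**Working it through.** **Inputs**
- Enrolled: 50 (Sample Size).
- Evaluable: 40 (Sample Size: "an evaluable sample of 40 subjects will provide 80% power to detect a difference of 10" per cent).
- Attrition allowed for: up to 20% (Sample Size).
- Scheduled adverse event assessments: one, at the End of Study Visit.
- Not in the documents: how many subjects non-evaluable for LDL-C still attend the virtual visit, and any adverse event rate.

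**The plan's own figure.** Evaluable number divided by the retained fraction: 40 / (1 − 0.20) = 50. This reproduces the stated enrollment exactly.

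**How many might not be asked.** Attrition at the ceiling is 50 − 40 = 10 subjects, or 10/50 = 20%. This allowance is for the LDL-C test. A subject without a final LDL-C value may still attend the virtual visit and be asked. If k of the 10 attend, and all 40 evaluable subjects are assumed to attend, the number not asked is 10 − k:

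| k attending (assumed) | Not asked | Share of 50 |
|---|---|---|
| 0 | 10 | 20% |
| 5 | 5 | 10% |
| 10 | 0 | 0% |

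**Who is and is not reached**
- Completes dosing and attends the final visit: asked once.
- Stops the product but attends the final visit: asked about events, but no listed item records why they stopped.
- Leaves before the final visit: asked about neither.

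**What this does to a safety statement.** Suppose no events are reported. The one-sided 95% upper bound on the event rate is 1 − 0.05^(1/n). With n = 50 asked it is 5.8%; with n = 40 asked it is 7.2%. The loss of precision is small. The 7.2% also assumes that those not asked resemble those asked, which is doubtful for subjects who stopped early. I put no number on the resulting understatement, because the documents give no event rate.

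**The case against.** The case for leaving the plan alone has substance.

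- **Low expected risk.** Purpose says that "the safety and benefits of plant sterol supplements have been established". Exclusion Criteria remove anyone who meets this description: "Subject has a known allergy or sensitivity to soy, corn, or other ingredients in the study product". They also remove pregnancy, active angina needing urgent work-up or intervention, uncompensated heart failure and undue risk as the investigator judges it. This limits the weight of the point. It does not cover a first reaction during dosing, since only known sensitivity is excluded.
- **Other contacts exist.** The Clinic describes physician visits and adds: "The patients also benefit from frequent dietitian/health coach visits during the program". These contacts have no written adverse event task, so they soften the gap without closing it.
- **Instructions may exist elsewhere.** The Baseline visit list includes instructing the subject, and the content is not shown. Consent pages were removed from this copy. Either may tell subjects whom to call. That would be a reporting route, but still not a step that asks those who leave.
- **The number may be zero.** This stands: the range runs from 0 to 10.

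Two stronger readings are tempting. A reader might infer that the trial has no way of learning of events before the end. The documents show only that no earlier solicitation is scheduled. A reader might also infer that an event on day 7 goes unnoticed for 90 − 7 = 83 days and that a weekly symptom question is needed. Those 83 days measure the delay to formal solicitation, not to the clinic hearing of the event. A weekly item is also a real trade-off: staff must review the replies, minor complaints cannot be attributed to the product without a control arm, and the prompts might influence compliance.

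**Conclusion.** The point holds as a low-cost improvement to consider. The schedule as written leaves subjects who depart before the final visit unasked about adverse events and about why they stopped. At the planned attrition ceiling that is 0 to 10 of 50 subjects (0% to 20%). The range assumes that attrition does not exceed 20% and that every LDL-C-evaluable subject attends the virtual visit; the position within it depends on attendance figures the documents do not give. Confidence is medium, because routine contacts or instructions not shown may capture some events.

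A reader might infer that the LDL-C finding is compromised. It is not: the gap concerns safety capture only, and closing it changes neither the sample size, the power nor the paired analysis. Nor do the documents support a claim that any particular number of events would be missed.

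**What to change.** 1. When a subject reports stopping the product or withdraws, the existing research team makes one text or phone contact and records adverse events and the reason for stopping.
2. The report gives adverse events for all subjects who took at least one dose, with the number who could not be reached, so that the denominator is clear.

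Tying the contact to a reported stop or a withdrawal avoids having to interpret a missed reply or a low compliance digit.

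**Cost.** About 10 short contacts at the attrition ceiling, plus one for each subject who stops the product but stays in the study. The research team already messages subjects every week, so no new channel is needed. The gain is limited to those who can be reached: some subjects lost to follow-up will not respond, and they should be counted as such. No added weekly symptom question is proposed.

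### Inclusion criterion 2 lets one LDL-C value both qualify a subject and serve as baseline for the single-arm primary outcome, so part of a measured fall may be regression to the mean

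*Combined protocol and SAP*

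**What the plan says.** Inclusion Criteria, item 2, sets the LDL-C range and names two acceptable sources for the value: "Subject has LDL-C ≥ 120 and < 190 mg/dL measured in the past 3 months (or measured at the baseline visit". It also requires the value to be off cholesterol-lowering treatment for at least a month. Item 3 uses the same range without naming a source. Item 4 admits subjects with LDL-C above 189 mg/dL, or with ASCVD risk above 7.5%, who have declined prescription treatment.

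Study Design describes the trial thus: "This single arm study will include one in-person or video baseline visit". On timing it says: "A fasting blood draw for baseline labs will be performed within 8 weeks of start date". The Baseline visit list contains both the eligibility review and "Fasting Lipid profile". The Primary Outcome is the percentage "change in LDL Direct, or LDL-C if LDL Direct is not available, from baseline at 3 months". The Statistical Analysis section tests it with a paired test. The plan does not say which value is baseline when an earlier one exists, gives no repeat or averaged baseline, and does not mention regression to the mean.

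**The concern.** When a subject is admitted because a measurement is high enough, that measurement tends to overstate the subject's usual level. A second measurement will on average be lower even if nothing has been done. If the first measurement is also the baseline, the drop is counted as change. A control arm would show the same drop and cancel it, but this trial has none.

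Criterion 2 allows this for anyone who qualifies at the baseline visit. It could also happen if a recent clinic value, drawn inside the 8-week window, were reused as baseline, for example when the visit is by video. The text neither provides for that reuse nor rules it out. At stake is whether the paired test could declare a reduction with an inactive supplement, and whether a reader of the results could tell.

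**Working it through.** **Inputs from the documents.** Window 120 to <190 mg/dL (criterion 2). SD 25 mg/dL, 40 evaluable, target 10%, two-sided alpha 0.05 (Sample Size, Statistical Analysis).

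**Assumptions.** Clinic mean μ 110-150 mg/dL, test-retest correlation ρ 0.7-0.9, normal values, no true effect, and the share of subjects with one value in both roles. The SD of 25 is taken as that of the unselected clinic population. A normal distribution cut to 120-190 cannot have an SD above 70/√12 = 20.2, so 25 is unlikely to describe the selected range alone. Subjects entering under criterion 4 could widen the enrolled spread, so this supports the assumption without proving it.

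**Step 1: the plan's own figure.** 40/(1 - 0.20) = 50 reproduces. The 40 cannot be checked, because neither the mean LDL-C nor the SD of change is given. The present point does not depend on it.

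**Step 2: expected fall by formula.** With a = (120 - μ)/25 and b = (190 - μ)/25:

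- selected mean = μ + 25 × [φ(a) - φ(b)] / [Φ(b) - Φ(a)]
- expected fall = (1 - ρ) × (selected mean - μ)

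For μ = 120 and ρ = 0.8, the selected mean is 139.65 and the fall is 0.2 × 19.65 = 3.93 mg/dL, or 3.93/139.65 = 2.8%. For μ = 150 and ρ = 0.8, the fall is only 0.50 mg/dL, because the upper limit nearly offsets the lower one.

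**Step 3: simulation of the percentage-change test.** The test is a one-sample t-test on percentage change, n = 40, with selection on 120 to <190. Subjects not sharing have a separate baseline draw. Each range runs from ρ = 0.9 to ρ = 0.7.

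| Clinic mean | All share: change; false significance | 30 of 40 share | 20 of 40 share |
|---|---|---|---|
| 110 | -1.9% to -5.6%; 30-74% | -1.3% to -3.9%; 17-40% | -0.8% to -2.2%; 9-16% |
| 120 | -1.3% to -4.0%; 18-46% | -0.9% to -2.7%; 11-23% | -0.5% to -1.4%; 7-10% |
| 130 | -0.8% to -2.5%; 10-22% | -0.5% to -1.6%; 7-12% | -0.2% to -0.7%; 6-7% |
| 140 | -0.4% to -1.2%; 6-9% | 5-6% | 5% |
| 150 | 0.0% to -0.1%; 5% | - | 5% |

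With a quarter sharing at means 110-130, the change is +0.2% to -0.5% and false significance 5-6%. False significance passes 10% only when about 18-22 of 40 share (mean 110), 20-30 (mean 120) or 28-40 (mean 130). At mean 140 it never does.

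**Step 4: variations.**

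- *Different assay.* Criterion 2 refers to LDL-C, the primary outcome prefers LDL Direct, and the Exploratory Outcomes list "Calculated LDL-C or LDL Direct". If the qualifying value is calculated and the outcome is direct, with an assumed same-draw correlation of 0.95, the factor (1 - ρ) becomes (0.95 - ρ). The 3.93 mg/dL becomes 0.15 × 19.65 = 2.95. With all sharing at means 110-130 the change is -0.3% to -4.5% and false significance 6-53%.
- *Separate qualifying and baseline draws.* The mean change in mg/dL is about 0 throughout. The mean of individual percentage changes is +0.3% to +1.2%, because a noisy baseline is the divisor.
- *Separate draws, range applied again at baseline.* Applying both limits brings back -0.4% to -3.4% at means 110-130. Applying only the upper limit gives +0.4% to +1.3% at means 110-150, so the false fall comes from the floor.
- *Criterion 4, LDL-C above 189.* If that draw is also baseline, the change within the group is about -2.5% to -13%. Under the same assumptions the group is only 0.2-7% of those selected on LDL-C.

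**The case against.** The strongest reply is that the size is unknown and the wording leans to the mild end. The share of subjects, the clinic mean and the correlation are all assumed. Criterion 2 puts the earlier value first and the baseline visit in parentheses. The Clinic section describes serial laboratory testing, so many subjects probably have an earlier result. The Baseline visit list has its own fasting lipid profile, naturally read as the baseline draw. Subjects who qualify on an earlier value and have that draw taken are largely protected. Those entering under criterion 4 on ASCVD risk alone face no LDL-C floor. All of this stands, and it is why no single figure can be given.

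A reader might infer that every subject's baseline is the qualifying value, or that the trial's false-positive rate is as high as 74%. The documents support neither. The 74% needs all 40 subjects sharing one draw, a clinic mean of 110 and a correlation of 0.7. Routine reuse of earlier results as baseline is likewise inferred only from silence about the 8-week window.

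It can also be said that the gain is limited, because coaching confounds the result anyway: "The patients also benefit from frequent dietitian/health coach visits during the program". That is true, but it does not remove a second source of apparent change that is cheap to reduce and to count.

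**Conclusion.** The point holds in conditional form, with moderate confidence, and should be fixed. The text permits one value to select a subject and to anchor the primary outcome, and the single-arm paired analysis cannot separate the resulting fall from an effect of the supplement.

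The consequence ranges from nil to serious. It matters if about half or more of the subjects share one draw and the clinic mean is near or below 120 mg/dL, or if most share at a mean of about 130. It is small or nil if few share or the mean is about 140 or higher. Even the worst case examined, -5.6%, is below the 10% target, so the documents do not support saying that a fall of the planned size would be wholly artefact. Because the plan asks for no count of these subjects, a reader of the results could not tell which case applies.

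**What to change.** 1. Where a subject has an LDL-C from the past 3 months that already meets criterion 2's off-treatment condition, apply the lower LDL-C limit to that value. Take the separate fasting lipid profile already listed at the baseline visit as baseline for the primary outcome, and do not apply the 120 mg/dL floor again to that draw. Leave the upper limit and criterion 4 as the plan states them.
2. Keep subjects whose qualifying LDL-C is also the baseline value, whichever LDL-C route they entered by (criteria 2, 3 or 4). Flag them, report how many there are, and give the primary result with and without them.

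**Cost.** Some wording in the protocol and analysis plan, and one flag per subject. The planned baseline draw must actually be taken instead of an earlier result being reused, which matters most for video visits. Fasting is already expected: "Subject is willing to fast (10-14 h, target 12 h, water only) prior to each clinic visit". Subjects with an earlier value below 120 and a baseline-visit value of 120 or more would no longer enter through criterion 2, so recruitment may slow slightly.

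The analysis without flagged subjects is less precise. With an SD of percentage change of about 8 to 15 points (from the simulation), the 95% half-width t × SD/√n is 2.6-4.8 points with 40 subjects, 3.0-5.6 with 30 and 3.7-7.0 with 20. The comparison will therefore not resolve a bias of 1-3%, and the count is the more informative output. Regression to the mean in flagged subjects stays in the full analysis, and confounding by the dietitian and coaching programme is untouched.
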